19.3. Risks associated with the Study Devices

[REDACTED]

If the subject's pain had improved while a test configuration is turned on during the study Programming Visit, there is a risk that some or all of this improvement may be lost when the test configuration is stopped.

The study device has no other incremental risks beyond other similar market-available external Spinal Cord Stimulation products.

19.4. Risks associated with Participation in the Clinical Study

The subject might find it difficult, uncomfortable, or tiresome to complete study visits and/or questionnaires.

If additional radiographic imaging is performed per study recommendation, the subject will have additional radiation exposure. However, clinical harm from the typical amount of radiation exposure is extremely rare.

19.5. Possible Interactions with Concomitant Medical Treatments

No possible interactions have been identified for use of the SCS system concomitant with any specific medications. However, there may be some risk that is unknown.

Medical treatments that should not be used while the SCS lead remains implanted are listed in the BSC directions for use for the applicable commercially approved lead(s).

19.6. Risk Minimization Actions

Additional risks may exist. Risks can be minimized through compliance with this protocol, performing procedures in the appropriate hospital environment, adherence to subject selection criteria, close monitoring of the subject's physiologic status during research procedures and/or

follow-ups and by promptly supplying BSC with all pertinent information required by this protocol.

All efforts will be made to minimize the aforementioned potential risks using the following approaches:

- Selection of Investigators (anesthesiologists and neurosurgeons) who are experienced and skilled in the treatment of subjects as per BSC's site selection and qualification procedures
- Clearly defined inclusion and exclusion criteria that ensure only appropriate subjects are enrolled
- Ensuring that treatment and follow-up of subjects is consistent with current medical practice
- Ensuring that both the Multichannel Stimulus Generator System and Modified OMG are only operated during the study Programming Visit by authorized BSC personnel in a study physician's office under the direct supervision of a study healthcare professional.

- Safety review processes by Boston Scientific
- Monitoring visits as needed

19.7. Anticipated Benefits

The reported benefit of the implementation of the Blue Box Study SCS System into future commercially available SCS may include:

- Reduction in the intensity of chronic low back pain
- Reduction in the intensity of chronic leg pain
- Reduction in overall pain (low back and/or leg pain)
- Improvement in physical functioning (disability)
- Improvement in sleep
- Improvement in quality of life
- Reduction in pain-related medication use

19.8. Risk to Benefit Rationale

The risk evaluation for the study determined that all hazards attributed to the Blue Box Study SCS System and overall remaining residual risks after implementations of the required mitigations have been evaluated. Based on the risk evaluation results, the potential future benefit provided by the Blue Box Study SCS System to treat chronic intractable pain of the trunk and limbs outweighs the remaining residual risk. As the overall residual risk meets BSN's criteria, the Blue Box Study SCS System is acceptable for use in a clinical setting.

19.9. Warnings and Precautions

To avoid possible complications, be sure to review warnings and precautions section of the directions for use manuals.

20. Safety Reporting**20.1. Reportable Events by investigational site to Boston Scientific**

It is the responsibility of the investigator to assess and report to BSC any event which occurs in any of following categories:

- All Serious Adverse Events
- All Investigational Device Deficiencies
- Unanticipated Adverse Device Effects/Unanticipated Serious Adverse Device Effects
- New findings/updates in relation to already reported events
- All Device Related Adverse Events evaluated by an investigator as clinically significant
- All Study Procedure Related Adverse Events evaluated by an investigator as clinically significant

When possible, the medical diagnosis should be reported as the Event Term instead of individual symptoms.

If it is unclear whether or not an event fits one of the above categories, or if the event cannot be isolated from the device or procedure, it should be submitted as an adverse event and/or device deficiency.

Any AE event required by the protocol, experienced by the study subject after informed consent and once considered enrolled in the study (as defined in study subject classification section), whether during or subsequent to the procedure, must be recorded in the CRF.

Underlying diseases are not reported as AEs unless there is an increase in severity of frequency during the course of the investigation. Death should not be recorded as an AE, but should only be reflected as an outcome of ONE (1) specific SAE (see Table 20.2-1 for AE definitions).

Refer to Section 18 for the known risks associated with the study devices.

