Blue Box Study
Study to Characterize the Effects of Programming Spinal Cord Stimulation (SCS) in
Patients Undergoing a Boston Scientific (BSC) SCS Temporary Trial

CLINICAL INVESTIGATION PLAN

Sponsored By

Boston Scientific Corporation
Neuromodulation
[name]
[name]
United States of America

This protocol contains confidential information for use by the Investigators and their designated representatives participating in this clinical investigation. The protocol should be held confidential and maintained in a secure location.

Do not copy or distribute without written permission from Boston Scientific Corporation.

THESE DOCUMENTS ARE THE PROPERTY OF BOSTON SCIENTIFIC CORPORATION AND SHALL NOT BE REPRODUCED, DISTRIBUTED, DISCLOSED OR USED FOR MANUFACTURE OR SALE OF APPARATUS WITHOUT THE EXPRESS WRITTEN CONSENT OF BOSTON SCIENTIFIC CORPORATION.

Contact Information

Role	Contact
Clinical Contact	[name], M.S. Principal Clinical Research Scientist Boston Scientific Corporation Neuromodulation [name] [name] United States of America [contact] [name]
Coordinating Principal Investigators	Not applicable

Revision History

	Release Date	
	May 18, 2016	
	September 29, 2016	
	June 14, 2019	

2. Protocol Synopsis

Blue Box: Study to Characterize the Effects of Programming SCS in Patients Undergoing a BSC SCS Temporary Trial	
Primary Objective	To characterize the effects of programming patterned SCS pulse trains in patients undergoing a Boston Scientific (BSC) SCS temporary trial.
Test Device	
 All BSC commercially approved Spinal Cord Stimulation SCS trial systems connected to BSC lead(s) [REDACTED]
Study Design	Prospective, multi-center, non-randomized, exploratory, single-arm
[REDACTED]	
[REDACTED]	Up to 3 sites in the US
[REDACTED]	

Blue Box: Study to Characterize the Effects of Programming SCS in Patients Undergoing a BSC SCS Temporary Trial	
	[REDACTED]
Safety Parameters	All device-related and procedure-related adverse events, all serious adverse events and serious adverse device effects will be reported from the time of enrollment until the end of study participation.
Follow-up Schedule	Study assessments will be required, as appropriate, at the following time points: 
 • Screening Visit (up to 14 days prior to Programming Visit) • Programming Visit (Day 0)

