At the time when the study-wide cap of 35 enrolled subjects is reached, further enrollment into the study will cease. The sponsor will notify all centers when approximately 30 subjects have been enrolled to alert investigators that enrollment will soon cease. The correspondence may also outline the specific activities to minimize the risk of enrollment after the protocol-specified cap of 10 enrolled subjects has been reached.

10.5. *End-of-Study Action Plan*

Subjects will be followed according to standard, routine medical care.

11. Study Methods

11.1. *Data Collection*

The table below illustrates the data that will be collected during the study visit.

Table 11.1-1: Data Collection Schedule

	Screening (≤ 14 Days prior to Day 0)	Programming Visit (Day 0)
Inclusion/Exclusion Criteria Evaluation	X	
Informed Consent (ICF)	X	
Demographics	X	
Medical History	X	
Adverse Events Assessment	X ¹	X
Imaging		X ²
Pain Drawing		X
Pain Intensity		X
Programming		X
Paresthesia Drawing		X ^{3,5}

Stimulation Questionnaire		X ³
Audio Recording		X ⁴

¹ AEs specified in Section 19 must be reported only after signing written informed consent.

² Optional.

³ Complete based on each selected test configuration setting

⁴ Optional Audio recording. Subjects will be asked to have their verbal description of the test configuration sensations recorded on audio. Subjects will be informed that they may refuse permission without penalty.

⁵ Optional Paresthesia Drawing

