20.4. Investigator Reporting Requirements

The communication requirements for reporting to BSC are as shown in Table 20.4-1.

All device-related and procedure-related adverse events, serious adverse events and serious adverse device effects will be reported from the time of enrollment until the end of study participation.

Table 20.4-1: Investigator Reporting Requirement:

Event Classification	Communication Method	Communication Timeline pre-market studies*	Communication Timeline post-market studies**
Unanticipated Adverse Device Effect /	Complete applicable CRF page(s) with all available new and	
 • Within 1 business day of first becoming aware of the event. 	
 • Within 1 business day of first becoming

Table 20.4-1: Investigator Reporting Requirement:

Event Classification	Communication Method	Communication Timeline pre-market studies* (MEDDEV 2.7/3 (2015): CLINICAL INVESTIGATIONS: SERIOUS ADVERSE EVENT REPORTING UNDER DIRECTIVES 90/385/EEC AND 93/42/EEC)	Communication Timeline post-market studies** (MEDDEV 2.12/2 rev.2 (2012): GUIDELINES ON A MEDICAL DEVICE VIGILANCE SYSTEM)
Unanticipated Serious Adverse Device Effect	updated information and fax to [contact] or email to [contact]	
 Reporting required through the end of the study participation 	
aware of the event.
 
 Terminating at the end of the study
Serious Adverse Event	Complete applicable CRF page(s) with all available new and updated information and fax to [contact] or email to [contact]	
 Within 3 calendar days of first becoming aware of the event or as per local/regional regulations. Reporting required through the end of the study participation 	
 Within 10 business days after becoming aware of the event or as per local/regional regulations. For Austria: within 2 business days of first becoming aware of the event. Reporting required through the end of study
	Provide all relevant source documentation (unidentified) for reported event upon request of the sponsor	
 At request of sponsor 	
 When documentation is available

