Serious Adverse Device Effects	Complete applicable CRF page(s) with all available new and updated information and fax to [contact] or email to [contact]	
 Within 3 calendar days of first becoming aware of the event or as per local/regional regulations. Reporting required through the end of the study participation 	
 Within 2 business days of first becoming aware of the event or as per local/regional regulations. Reporting required

Table 20.4-1: Investigator Reporting Requirement:

Event Classification	Communication Method	Communication Timeline pre-market studies*	Communication Timeline post-market studies**
			through the end of the study

Investigational Device Deficiencies (including but not limited to failures, malfunctions, and product nonconformities)
 
Note: Any Investigational Device Deficiency that might have led to a serious adverse event if a) suitable action had not been taken or b) intervention had not been made or c) if circumstances had been less fortunate is considered a reportable event.
	
Investigational Devices only: Complete applicable CRF page(s) with all available new and updated information and fax to [contact] or email to [contact]
	
 • When documentation is available • Within 3 calendar days of first becoming aware of the event. • Reporting of investigational device deficiencies required through the end of the study participation 	
 • When documentation is available • Within 2 business days of first becoming aware of the event. Reporting required through the end of the study
Adverse Event including Adverse Device Effects	Complete AE CRF page, which contains such information as date of AE, treatment of AE resolution, assessment of seriousness and relationship to the device.	
 • In a timely manner (e.g. Recommend within 10 business days) after becoming aware of the information • Reporting required through end of the study participation 	
 • In a timely manner (e.g. recommend within 30 business days) after becoming aware of the information • Reporting required through end of study

Table 20.4-1: Investigator Reporting Requirement:

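### Section 20.1 asks sites for only those non-serious related AEs the investigator judges clinically significant, while the synopsis and Section 20.4 ask for all of them

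*Combined protocol and SAP*

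**What the plan says.** The synopsis, under Safety Parameters, states: "All device-related and procedure-related adverse events, all serious adverse events and serious adverse device effects will be reported from the time of enrollment", running to the end of study participation. Section 20.4 repeats the scope almost word for word: "All device-related and procedure-related adverse events, serious adverse events and serious adverse device effects will be reported from the time of enrollment". Table 20.4-1 then has a row headed "Adverse Event including Adverse Device Effects", with timelines but no severity or significance condition.

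Section 20.1, which tells the site what to assess and report to the sponsor, is narrower for two categories: "All Device Related Adverse Events evaluated by an investigator as clinically significant" and "All Study Procedure Related Adverse Events evaluated by an investigator as clinically significant". The other categories in that list (serious events, investigational device deficiencies, unanticipated device effects, updates to earlier reports) carry no such condition. A fallback for doubtful cases follows: "If it is unclear whether or not an event fits one of the above categories, or if the event cannot be isolated from the device". Such events, and those that cannot be separated from the procedure, are to be submitted as well.

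Note 5 to Section 20.2 says that sensations or side effects during the programming session are not reported as AEs, but that those persisting or arising after programming are. Footnote 1 of Table 11.1-1 says: "AEs specified in Section 19 must be reported only after signing written informed consent".

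**The concern.** Related adverse events are the safety parameter named in the synopsis. Section 20.1 is the list a coordinator is most likely to work from when deciding whether to complete a form, and it passes those events through an individual judgement for which the protocol sets no standard. Note 7 to Section 20.2 uses the same term for worsening of baseline pain but does not define it there either. No visible text says which scope prevails.

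If one site follows 20.1 and another follows 20.4, the same mild related event is recorded at one and not at the other. The pooled count would then be lower than the parameter described, and a difference between the sites (up to three) could reflect reading habits rather than anything about the device. The sponsor's early safety review in Section 22.1 depends on what sites submit.

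**Working it through.** The protocol states no related-AE rate or count, so there is no figure to reproduce. The check is a comparison of rules, followed by a scale calculation.

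**1. One test event under each rule.** Take a non-serious, device-related side effect that persists after programming ends and that the investigator clearly judges not clinically significant.

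- Synopsis, Safety Parameters: reportable (related, no filter).
- Section 20.4, opening text: reportable (same wording).
- Table 20.4-1, adverse event row: reportable (no filter).
- Section 20.2, Note 5: reportable (persists after the session).
- Section 20.1, device-related bullet: not on the list.
- Section 20.1, fallback: does not apply. The fallback covers doubt about whether an event fits a category, or an event that cannot be separated from the device or procedure. Here there is no doubt; the judgement has been made.
- Section 20.1 on CRF recording, and Section 17.2: no help. Both refer to events as the protocol requires, which is the point in dispute.

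The event is called for in four places and missing from the list in the fifth.

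**2. What is not affected.**

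- SAEs, and therefore SADEs: unfiltered in 20.1.
- UADEs/USADEs: unfiltered in 20.1.
- Investigational device deficiencies: unfiltered in 20.1.
- Sensations during programming: excluded by Note 5 under either rule.

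What remains is non-serious related events that persist or start after programming, or that otherwise occur between consent and the end of participation. Under Sections 10.3 and 11.5 participation normally ends with the Programming Visit, or at most 15 days after screening if that visit is not completed. The window is short.

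**3. Scale.** Inputs: the enrollment cap of 35 in Section 10.4. The same paragraph also mentions a cap of 10.

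- Subject-level rate with x affected subjects: x/n. If one subject's only related event is dropped, the rate becomes (x − 1)/n, a fall of 1/n.
- n = 35: 1/35 = 0.0286, or 2.9 percentage points.
- n = 10: 1/10 = 0.10, or 10 percentage points.

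For event counts, let N be the number of non-serious related events reportable under 20.4 and s the share judged clinically significant. The 20.1 count is s × N. The documents do not give s. As an assumption, s from 0.25 to 1.0 gives 25% to 100% of the 20.4 count; at s = 1.0 there is no gap. N is not given either, so no total can be calculated.

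**The case against.** The best case for leaving the text alone is that 20.1 sets a minimum. It does not say that only the listed events may be reported, and a site that reports every related event under 20.4 satisfies both sections. A reader might infer that the rules cannot all be followed; that is not so. What stands is that a site following the 20.1 list alone falls short of the synopsis and 20.4.

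A reader might also take the frequency bands in Section 19.2 as the size of the problem: undesirable sensations in at least 50% of patients (35 × 0.50 = 17.5, so 18 subjects) and overstimulation in at least 20% (35 × 0.20 = 7). The documents do not support this. Section 19 says the bands describe typical SCS use and likely overestimate risk here. Note 5 removes in-session sensations under both rules. No persistence rate is given, and nothing states how many such events would be judged insignificant.

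Footnote 1 of Table 11.1-1 could be read as a third reporting scope, limited to the anticipated events of Section 19. It is more likely a stale cross-reference. Its purpose is timing relative to consent, and 20.1 similarly sends the reader to Section 18 for known risks that now sit in Section 19. A shift of one section number would explain both.

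Finally, the study is exploratory with no powered endpoint (Section 12), and relatedness is itself an investigator judgement under either rule. Both points are correct. They limit the consequence to the completeness and comparability of the AE listing, but they do not settle which events a site should send.

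**Conclusion.** The inconsistency is real and sits in current text; neither redaction nor an amendment log explains it. For non-serious device-related and procedure-related AEs, the 20.1 list is narrower than the safety parameter in the synopsis and 20.4, by a threshold that is not defined. Under-reporting at a site that relies on 20.1, and differences between sites, are possible consequences; the documents do not show that either will occur.

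The size is unknown and probably small in number of events, given the short observation window and Note 5. The figure of 2.9 percentage points per dropped subject assumes that 35 subjects are enrolled and that a subject-level rate is reported, which the visible text does not specify. A reader might infer that the safety data as a whole are compromised; the unfiltered reporting of SAEs, UADEs/USADEs and investigational device deficiencies rules that out. The change is worth making because it is cheap and bears directly on the stated safety parameter.

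**What to change.** Delete the clinical-significance condition from both the device-related and the study-procedure-related bullets in Section 20.1, so that the list matches the synopsis, Section 20.4 and Table 20.4-1. In footnote 1 of Table 11.1-1, change the reference from Section 19 to Section 20.

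If the sponsor meant the condition to apply, the text can instead be reconciled by defining the term and carrying it into the synopsis, 20.4 and the table row. That gives sites one rule but narrows the safety parameter, so deletion is preferable for completeness.

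The cost of deletion is a wording amendment, a few additional non-serious AE forms in at most 35 subjects, and possibly a slightly less favourable AE count.

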20.2. Definitions and Classification

Adverse event definitions are provided in Table 20.1. Administrative edits were made to combine definitions from ISO 14155-2011 and MEDDEV 2.7/3 (2015).

Table 20.1: Adverse Event Definitions	
Term	Definition

Adverse Event (AE)
 
Ref: ISO 14155-2011
 
Ref: MEDDEV 2.7/3 (2015)
	
Any untoward medical occurrence, unintended disease or injury, or any untoward clinical signs (including an abnormal laboratory finding) in subjects, users or other persons, whether or not related to the investigational medical device.
 
NOTE 1: This includes events related to the investigational medical device or comparator.
 
NOTE 2: This definition includes events related to the procedures involved.
 
NOTE 3: For users or other persons, this definition is restricted to events related to the investigational medical device.

Adverse Device Effect (ADE)
 
Ref: ISO 14155-2011
 
Ref: MEDDEV 2.7/3 12/2010
	
Adverse event related to the use of an investigational medical device
 
 • NOTE 1: This definition includes any adverse event resulting from insufficient or inadequate instructions for use, the deployment, the implantation, the installation, the operation, or any malfunction of the investigational medical device. • NOTE 2: This definition includes any event resulting from use error or from intentional misuse of the investigational medical device.

Serious Adverse Event (SAE)
 
Ref: ISO 14155-2011
 
Ref: MEDDEV 2.7/3 12/2010
	
Adverse event that:
 
 • Led to death, • Led to serious deterioration in the health of the subject, that either resulted in: 
 ○ a life-threatening illness or injury, or ○ a permanent impairment of a body structure or a body function, or ○ in-patient or prolonged hospitalization of existing hospitalization, or ○ medical or surgical intervention to prevent life-threatening illness or injury or permanent impairment to a body structure or a body function • Led to fetal distress, fetal death, or a congenital abnormality or birth defect. 
NOTE 1: Planned hospitalization for a pre-existing condition, or a procedure required by the clinical investigational plan, without serious deterioration in health, is not considered a serious adverse event.


Serious Adverse Device Effect (SADE)
 
Ref: ISO 14155-2011
 
Ref: MEDDEV 2.7/3 12/2010
	
Adverse device effect that has resulted in any of the consequences characteristic of a serious adverse event.

Unanticipated Adverse Device Effect (UADE)
 
Ref: 21 CFR Part 812
	
Any serious adverse effect on health or safety or any life-threatening problem or death caused by, or associated with, a device, if that effect, problem, or death was not previously identified in nature, severity, or degree of incidence in the investigational plan or application (including a supplementary plan or application), or any other unanticipated serious problem associated with a device that relates to the rights, safety, or welfare of subjects.

Unanticipated Serious Adverse Device Effect (USADE)
 
Ref: ISO 14155-2011
 
Ref: MEDDEV 2.7/3 (2015)
	
Serious adverse device effect which by its nature, incidence, severity, or outcome has not been identified in the current version of the risk analysis report.
 
NOTE 1: Anticipated serious adverse device effect (ASADE) is an effect which by its nature, incidence, severity or outcome has been identified in the risk analysis report.

Device Deficiency
 
Ref: ISO 14155-2011
 
Ref: MEDDEV 2.7/3 12/2010
	
A device deficiency is any inadequacy of a medical device with respect to its identity, quality, durability, reliability, safety or performance.
 
NOTE 1: Device deficiencies include malfunctions, misuse or use errors, and inadequate labeling.

Abbreviations: EC=Ethics Committee; IRB=Institutional Review Board
	

NOTES:

1. For the purposes of this study, hospitalization is defined as any in-patient admission.
2. Hospitalizations occurring for the purpose of performing a planned procedure as per routine care such as implant procedures are not to be reported as a SAE. However, complications or adverse events that occur during the planned procedure should be reported as (S)AEs if they meet the protocol specified definitions.
3. Elective/planned hospitalization(s) need not be reported as an SAE. However, complications or adverse events that occur during an elective/planned hospitalization, should be reported as (S)AEs if they meet the protocol specified definitions.
4. In the event of subject death during the conduct of the study, efforts should be made to perform an autopsy.
5. Sensations or side effects that occur during the programming session should not be reported as AEs. However, sensations or side effects that persist or occur after the completion of the programming will be reported as AEs.
6. Lack of efficacy/decreased therapeutic response will not be collected as AEs. Also, return of the patient's pain symptoms to their Baseline level does not meet the criteria for an AE.
7. Clinically significant worsening of the pattern of intensity or distribution of Baseline pain symptoms or other sequelae as a result of lack of efficacy/decreased therapeutic response should be reported as an AE.
8. Device/lead migration will not be collected as an AE. However, if the device/lead migration precipitated an AE, the AE should be reported in the *Adverse Event* CRF. Device/lead migration should be documented in the *Device Deficiency* CRF.
9. Device deficiencies, failures, malfunctions, and product nonconformities should not be reported as adverse events. However, if an adverse event resulted from a device failure or malfunction, that specific event would be recorded on the *Adverse Event* CRF. Device deficiencies, failures, malfunctions, and product non-conformities should be documented in the *Device Deficiency* CRF.

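### Note 5 in Section 20.2 keeps clinically significant effects that resolve within the programming session out of adverse event reporting, in conflict with Section 20.1

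*Combined protocol and SAP*

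**What the plan says.** Note 5, in the notes after Table 20.1 in Section 20.2, reads: "Sensations or side effects that occur during the programming session should not be reported as AEs". Its second sentence restores some effects by timing alone: "sensations or side effects that persist or occur after the completion of the programming will be reported as AEs".

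Section 20.1 lists what the site must report to the sponsor. Two of its categories are "All Device Related Adverse Events evaluated by an investigator as clinically significant" and "All Study Procedure Related Adverse Events evaluated by an investigator as clinically significant". It adds that an event the protocol requires, "whether during or subsequent to the procedure, must be recorded in the CRF". It also has a default rule, opening "If it is unclear whether or not an event fits one of the above categories", under which doubtful events are submitted.

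The Safety Parameters row of the synopsis and the opening of Section 20.4 are wider. They call for all device-related and procedure-related adverse events, from enrollment to the end of participation, with no test of clinical significance.

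Note 7 in Section 20.2 does apply such a test, for pain symptoms: "Clinically significant worsening of the pattern of intensity or distribution of Baseline pain symptoms" is to be reported, although loss of efficacy is otherwise exempt under Note 6.

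**The concern.** Some exemption is sensible. Section 8.3 says the endpoints are meant to observe the paresthesia that programming produces, and reporting every expected tingle as an adverse event would serve nobody. But Note 5 covers side effects as well as sensations, and it does not separate expected, trivial effects from clinically significant ones.

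The setting makes this matter. The session that Note 5 exempts is the period in which the study device is used, and little observation follows it. Three things are at stake:

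- A low or zero count of device-related events could not be taken to mean that no clinically significant effects occurred while the study stimulator was running.
- Two sites, each following the protocol, could record the same in-session event differently, one under Note 5 and the other under Section 20.1.
- The evaluation by the medical monitor and safety medical director (Section 22.1) depends on events being reported, so an exempted effect would not reach them as an adverse event.

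**Working it through.** The plan gives no figure to reproduce, so the check is a comparison of provisions.

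**1. Does the exemption cover the exposure period?** Section 19.6 confines operation of the study stimulator components to the Programming Visit. Section 11.5 follows a programmed subject only through that visit. The exempted session is therefore where the study device acts.

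**2. Are relevant effects foreseen?** Section 19.2 lists adverse device effects known to go with programming as done in this study. They include overstimulation with jolts or shocks, and muscle spasms. Such effects could begin and end within a session.

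**3. Does any definition exclude short-lived events?** No. The adverse event definition in Table 20.1 sets no minimum duration.

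**4. How does each provision treat the same event?**

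| Device-related event | Section 20.1 | Synopsis and 20.4 | Note 5 |
|---|---|---|---|
| Not clinically significant, resolves in session | Not required | Required if it is an adverse event | Not reported |
| Clinically significant, non-serious, resolves in session | Required | Required | Not reported |
| Clinically significant, continues after programming | Required | Required | Reported (second sentence) |
| Serious, resolves in session | Required | Required | Not reported, read literally |
| Clinically significant, due to malfunction, resolves in session | Required | Required | Not reported, but Note 9 restores it |

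The second row is the main conflict. The fourth is a small residue. Most consequences that make an event serious would outlast the session and be restored by Note 5's second sentence. One that might not is "medical or surgical intervention to prevent life-threatening illness or injury or permanent impairment to a body structure or a body function", where the event resolves fully in session. Unanticipated device effects and device deficiencies are separate reportable categories.

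**5. Do the neighbouring notes work the same way?** No. Notes 2 and 3 exempt planned procedures and hospitalizations but restore complications that meet the protocol's definitions. Note 7 restores clinically significant worsening. Notes 8 and 9 restore adverse events that arise from lead migration or malfunction. Only Note 5 restores by timing alone.

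**6. Is the information captured elsewhere?** Table 11.1-1 schedules an adverse event assessment at the Programming Visit, but Note 5 removes resolved in-session effects from it. A Stimulation Questionnaire is completed for each selected configuration (Section 11.4). It may record some sensations, but its content is not shown and it is not adverse event reporting.

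**7. Can the loss be counted?** No. That would need the share of in-session effects that are clinically significant and the share of those that resolve in session. The documents give neither. The frequency bands in Section 19 apply to typical use of spinal cord stimulation and, by the protocol's own statement, probably overstate the risk here. Multiplying them by the enrollment number would count something else.

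**The case against.** The best counter-reading is that Note 5 is a deliberate, study-specific rule about what counts as an adverse event. It sits among notes that do that job, and a general duty narrowed by a specific note is ordinary drafting. The recording sentence in Section 20.1 covers only events the protocol requires, so it could be read as deferring to Note 5. That limit is real, and the during-or-after wording is therefore supporting evidence only. But it qualifies that one sentence. The two categories quoted from Section 20.1 themselves state what is required, and neither Section 20.1, Section 20.4 nor the synopsis refers to Note 5.

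The safeguards are also partial. Note 9 gives events caused by failure or malfunction an express route to the adverse event form, and Section 20.5 sends use errors to the sponsor as device deficiencies. Neither covers overstimulation while the device works as intended. The default for unclear events does not help a site that takes Note 5 at its word, because that site sees nothing unclear.

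Several limits stand. The residue is narrow, and injuries from overstimulation would often outlast the session and be reported. The unseen questionnaire means the true loss of information cannot be judged. The study is exploratory, with at most three sites and no powered endpoint, and no visible text plans to draw a conclusion from a low event count. The mismatch between *all* and *clinically significant* events would exist without Note 5 and adds nothing to the weight of this point.

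**Conclusion.** The conflict is real as written. Note 5 removes from adverse event reporting a class of event that Section 20.1, Section 20.4 and the synopsis require: device-related or procedure-related effects that are clinically significant and resolve within the session. The class is mainly non-serious and its size cannot be computed. The conclusion rests on the wording alone and needs no assumption about event rates. That such events may occur rests on the protocol's own list of programming effects. It should be fixed, because the exempted period is the period of study device use and the remedy is cheap.

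**What to change.** Reconcile the four places:

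- **Note 5.** Limit the exemption to stimulation sensations that resolve in session and are not clinically significant. Add that in-session effects that are serious, or that the investigator judges clinically significant, are reported when they meet the protocol's definitions. Section 20.1 already supplies that test, and Notes 2 and 3 already supply the form of words.
- **Synopsis, Section 20.1 and Section 20.4.** Use one scope, either all related events or clinically significant ones, and cross-reference the narrowed Note 5 in each. The cross-reference matters most if *all* is chosen, because the conflict would otherwise return.
- **Study report.** State that transient, non-significant in-session sensations were not counted as adverse events.

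This changes what is reported, not how subjects are managed. The cost is a set of wording edits, slightly more case report form work, an investigator judgement of clinical significance during the session, and possibly a less favourable adverse event count.
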